# 6.11 Electroretinography

Electroretinography testing of both eyes will be performed at the screening and baseline visits and at visits 3, 6 and 12 months after study agent administration, using both full-field (ffERG) and multifocal (mfERG) procedures.

# 6.12 Optical Coherence Tomography

Retinal anatomy will be evaluated by spectral domain optical coherence tomography (SD-OCT) scans of both eyes once at the screening visit, twice at the baseline visit, and once at visits 1, 2, 3, 6, 9 and 12 months after study agent administration. Additional SD-OCT scans may be obtained at the discretion of the investigator. Each SD-OCT will generate macula volume scans and high resolution horizontal and vertical scans centered on the fovea.

# 6.13 Fundus Photography

Fundus photography will be performed at the baseline visit and at the visit 12 months after study agent administration.

# 6.14 Quality of Life

For participants  $\geq$  16 years of age, quality of life will be assessed using the 25-Item National Eye Institute Visual Function Questionnaire (VFQ-25) [60]. The questionnaire will be administered in an interview format at the screening and baseline visits and at visits 3, 6, 9 and 12 months after study agent administration.. For participants <16 years of age, a pediatric quality of life questionnaire may be administered.

# 6.15 Long-term Follow-up

After the completion of 9 study visits over the course of one year after study agent administration, long-term follow-up will be conducted annually for an additional 4 years after the Month 12 visit. At each of these visits, testing will include clinical evaluation, visual acuity and ophthalmic examinations. In accordance with regulatory guidance for gene therapy clinical trials, information will also be obtained about any cancer, neurological, autoimmune or hematological disorder that developed or worsened since the last visit in the form of a long-term follow-up questionnaire. The questionnaire is provided in Appendix B.

# 7 ASSESSMENT OF SAFETY

# 7.1 Specification of Safety Parameters

#### 7.1.1 **Primary Endpoint**

The primary objective of this study is to evaluate the safety of rAAV2tYF-CB-hRS1 administered by intravitreal injection in patients with XLRS. The primary safety parameter will be the frequency of Grade 3 or 4 local (ocular) or systemic AEs that occur during the 12 months after study agent administration.

#### 7.1.2 Secondary Endpoints

Secondary safety parameters will include the following:

- The frequency of all AEs, including serious AEs,
- The frequency of abnormal hematology or clinical chemistry parameters,
- Changes in titers of serum antibodies or IFN-γ ELISPOT responses to RS1.

## 7.2 Assessing, Recording, and Analyzing Safety Parameters

Local (ocular) and systemic AEs will be assessed using CTCAE v4.0 criteria and recorded at every visit. Ophthalmic examinations, as described in Section 6.9, will be performed before and after study agent administration. Slit lamp biomicroscopy of anterior and posterior segment, tonometry and indirect ophthalmoscopy will be the principal method to detect ocular AEs.

Non-ocular AEs will be assessed by performing a medical history and physical examination before study agent administration, obtaining an interim medical history and symptom-directed physical exam at each visit after study agent administration, and performing tests of hematology and clinical chemistry before and after study agent administration as described in Section 6. Non-ocular AEs will be assessed by performing a medical history and physical examination before study agent administration, obtaining an interim history and physical examination before study agent administration, obtaining an interim history and symptom-directed physical exam at each visit after study agent administration, and performing tests of hematology and clinical chemistry parameters before and after study agent administration as described in Section 6.

Enrolled participants will have frequent follow-up visits during the first year after study agent administration. To monitor for delayed AEs and assess the duration of any visual changes that occur, long-term follow-up will be conducted annually for 4 years after completion of the Month 12 visit after the study drug administration. In accordance with regulatory guidelines for gene therapy clinical trials, at these visits, information will be obtained about any cancer, neurological, autoimmune or hematological disorder that developed or worsened since the last visit.

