### 6.9 **Ophthalmic Examinations**

Ophthalmic examinations of both eyes will be performed at the screening and baseline visits and at each visit after study agent administration, including each long-term follow-up visit. These examinations will include slit lamp examination, tonometry, indirect ophthalmoscopy and retinal biomicroscopy. Signs of inflammatory responses will be quantified using a standard 0 to 4+ cells and flare grading system [59]. On the visit at which the study agent is administered, IOP in the study eye will be measured about 30 minutes after study agent administration is completed.

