# 6.10 Visual Function Measurements

All visual function measurements will be obtained for both eyes at each visit when such testing is performed.

Best corrected visual acuity (BCVA) testing will be performed once at the screening visit, twice at the baseline visit, and once at each visit after study agent administration, including each longterm follow-up visit. BCVA will be determined using a standard Early Treatment of Diabetic Retinopathy Study (ETDRS) visual acuity testing protocol.

Visual field and microperimetry testing will be performed once at the screening visit, twice at the baseline visit, once at visits 1, 2, 3, 6, 9, and 12 months after study agent administration. Visual field testing will be performed using the Haag Streit Octopus 900 perimeter. Static perimetry will use the German Adaptive Thresholding Estimation (GATE) method and kinetic perimetry will use the Semi-automated Kinetic Perimetry (SKP) method. Microperimetry will be performed using the MP1 microperimeter.

Reading speed and contrast sensitivity testing will be performed once at the screening visit, twice at the baseline visit, and once at visits 3, 6, 9, and 12 months after study agent administration. Reading speed will be measured using MNREAD charts. Contrast sensitivity will be measured using Pelli-Robson charts.

Additional non-invasive measures of visual function may also be performed at the discretion of the investigator.

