#### 7.2.1 Adverse Events and Serious Adverse Events

#### 7.2.1.1 Definition of an Adverse Event

The International Conference on Harmonisation (ICH) E6 Good Clinical Practice (GCP) guidelines define an AE as "any untoward medical occurrence in a patient or clinical investigation subject administered a pharmaceutical product and which does not necessarily have a causal relationship with this treatment." An AE can therefore be any unfavorable and unintended sign (including an abnormal laboratory finding), symptom, or disease temporally associated with the use of a medicinal (investigational) product. The occurrence of an AE may come to the attention of study personnel during study visits and interviews or by a study recipient presenting for medical care. All AEs must be graded for intensity and relationship to study product.

An AE **does** include:

- Exacerbation of a pre-existing illness,
- An increase in frequency or intensity of a pre-existing episodic event or condition,
- A condition detected or diagnosed after study agent administration even though it may have been present prior to the start of the study,
- Continuous persistent disease or symptoms present at baseline that worsen following the start of the study.

An AE does not include:

- A medical or surgical procedure (e.g., surgery, endoscopy, tooth extraction, transfusion); the condition that leads to the procedure may be an AE,
- A pre-existing disease or conditions present or detected at the start of the study that does not worsen,
- Situations where an untoward medical occurrence has not occurred (e.g., normal pregnancy, hospitalizations for cosmetic elective surgery, social and/or convenience admissions),
- Overdose of either study agent or concurrent medication without any signs or symptoms.

AEs may include pre- or post-treatment events that occur as a result of protocol-mandated procedures (e.g., invasive procedures, modification of subject's previous therapeutic regimen). Intercurrent illnesses that occur after screening but before starting treatment, and that are not the result of protocol-mandated procedures, do not need to be captured as AEs.

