# 8.1 Specification of Efficacy Parameters

- Changes in best corrected visual acuity,
- Changes in the size of schisis cavities on OCT scans,
- Changes in ERG responses,
- Changes in static and kinetic visual fields,
- Changes in microperimetry,
- Changes in reading speed,
- Changes in contrast sensitivity,
- Changes in ffERG,
- Changes in mfERG,
- Changes in quality of life questionnaire responses.

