#### 10.7.2 Safety Analysis

Safety will be monitored by evaluation of ocular and non-ocular AEs and hematology and clinical chemistry parameters.

Adverse experiences will be coded into MedDRA preferred terms. The number and percentage of participants within each treatment assignment experiencing each specific adverse experience will be tabulated by intensity and by relationship to treatment. For the calculations in these tables, each participant's adverse experience will be counted once under the maximum intensity or the strongest recorded causal relationship to treatment.

A complete listing of serious adverse experiences for each participant will provide details including intensity, relationship to treatment, onset, duration and outcome.

Listings and descriptive statistics will be provided for each time point for all laboratory parameters.

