#### 10.7.3 Efficacy Analysis

Efficacy will be measured by evaluation of visual acuity, schisis cavity volume on OCT scans, static and kinetic visual fields measured using the Octopus perimeter, microperimetry, reading speed, contrast sensitivity, ERG, and quality of life questionnaires.

Visual acuity data will be presented as the ETDRS letter score at each time point.

Volumetric analysis of schisis cavity size will be quantified using a method developed at the Casey Eye Institute.

For visual fields, mean sensitivity, mean defect, square root of the loss variance, volume of full field hill of vision, 30 degree hill of vision, total volume loss, the area of kinetic perimetry isopters in mm^2, and the mean luminance sensitivity for the entire test field in decibel steradians, will be recorded for each eye and at each time point.

CONFIDENTIAL

For microperimetry, the equivalent of the 10-2 stimulus pattern will be used with a Nidek MP-1, microperimeter. The initial analysis will evaluate total sensitivity over time. Subsequent analyses will evaluate focal regions of change or point-by-point regression over time.

For reading speed, the reading acuity, critical print size and maximum reading speed will be recorded.

For contrast sensitivity, the number of letters read will be recorded.

The ffERGs responses will be analyzed by recording amplitude and implicit time measurements for each eye for standard ISCEV responses. Additional analyses to isolate the rod-only b-wave response may also be performed.

The mfERG responses will be analyzed by recording average latency and amplitudes for each of 6 standard rings for a 103 hexagon display.

Quality of life questionnaires will be scored using the NEI VFQ-25 scoring algorithm.

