15.1 Visual Acuity

BCVA testing will be performed once at the screening visit, twice at the baseline visit, and once at each visit after study agent administration, including each long-term follow-up visit. BCVA will be determined using a standard ETDRS visual acuity testing protocol.

The observed and change and percent change from baseline (average of the two baseline results) visual acuity will be summarized for each eye using continuous descriptive statistics by visit for each group and for all subjects. P-values from paired t-tests comparing post-baseline visits with baseline visit and p-values from 2-sample t-tests comparing study eye with fellow eye will be presented for Treatment Groups 2A, 2+2A, 4, 3+4, and all subjects combined. All inferential statistics are

exploratory in nature. Visual acuity data will be presented as the letter score and the logMAR (calculated as (85-ETDRS)/50, where ETDRS is the ETDRS/EVA letter score) at each time point. Change from baseline in ETDRS letter score will be summarized for the following categories: <=-15, -15 to <-8, -8 to <0, no change, >0 to 8, >=8 to 15, >=15. A subject listing of visual acuity will also be produced.

Box plots of change from baseline in ETDRS BCVA by visit will be presented by group and overall (one box for each group side-by-side at each visit) and repeated by eye (study eye and fellow eye).

Line plots of ETDRS BCVA letter score by visit with 95% confidence intervals (CIs) will be plotted by group and overall. Right and left eyes will be displayed side-by-side on the same page.

Histograms of ETDRS BCVA score at each visit by group and overall will be presented in panel graphs (one panel for each group by visit) and repeated by eye (study eye and fellow eye).

08 August 2017

Scatter plots of ETDRS BCVA score at follow-up visits versus baseline (also known as shift plots) by group and overall will be presented in panel graphs (one panel for each group by visit) and repeated by eye (study eye and fellow eye). A regression line and a line going through the origin will be overlaid in the scatter plots.

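### Visual acuity is measured at every scheduled visit after Day 0, but no safety table counts the participants who lost 15 or more letters at any time

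*Protocol*

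**What the plan says.** **Detection and safety analysis.** Protocol 7.2 states: "Slit lamp biomicroscopy of anterior and posterior segment, tonometry and indirect ophthalmoscopy will be the principal method to detect ocular AEs". Protocol 6.9 describes the ophthalmic examination without acuity: "These examinations will include slit lamp examination, tonometry, indirect ophthalmoscopy and retinal biomicroscopy". Protocol 10.7.2 gives the inputs to the safety analysis: "Safety will be monitored by evaluation of ocular and non-ocular AEs and hematology and clinical chemistry parameters". SAP 14.5 to 14.7 summarise slit lamp, tonometry and indirect ophthalmoscopy. For slit lamp and ophthalmoscopy the SAP tabulates shifts from baseline to the worst follow-up value.

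**Acuity.** Protocol 6.10 has BCVA measured in both eyes, "once at each visit after study agent administration"; the schedule shows none on Day 0. Protocol 8.1 lists it among the efficacy parameters ("Changes in best corrected visual acuity"), and 10.7.3 agrees: "Efficacy will be measured by evaluation of visual acuity, schisis cavity volume on OCT scans". SAP 3.2 makes it a secondary variable and SAP 15.1 places it in the efficacy section. There, "Change from baseline in ETDRS letter score will be summarized for the following categories: <=-15", followed by smaller losses, no change and gains. The output is Table 14.2.1.3, in the efficacy series. No table in the 14.3 or 14.4 safety series contains acuity.

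**Display rules.** SAP 9.4 presents summaries by group and, where appropriate, by visit, and does not summarise unscheduled visits.

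**Adverse event definition.** Protocol 7.2.1.1 counts as an AE: "Continuous persistent disease or symptoms present at baseline that worsen following the start of the study". No size of letter loss is given.

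**The concern.** The primary objective is the safety of an injection into one eye, and loss of acuity in that eye is a harm the trial measures repeatedly and on a numerical scale. A reader of the safety section will want to know how many participants had a large loss at some point after injection, and how many still had it at Month 12.

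The safety tables can answer only through AE recording. The efficacy table holds the measured losses but splits them by visit, so it cannot give a count of participants across visits. A loss measured at an unscheduled visit is not in it at all. Protocol 5.4 tells participants to report diminished vision at once, so such a visit is a plausible place for an acute loss to be measured.

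**Working it through.** **1. The plan's own precision figure.** The only numerical safety precision in the documents is the upper 95% limit for zero dose-limiting toxicities. The exact two-sided limit is 1 - 0.025^(1/n). For n = 9 it is 33.63% and for n = 27 it is 12.77%, both as stated in Protocol 10.5. This point does not depend on those figures. They show how coarse any count out of 27 will be.

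**2. What a by-visit table can tell.** Let M be the largest count in the <=-15 class at any one visit and S the sum of the counts over visits. The number of participants affected at any time lies between M and the smaller of S and 27. Suppose the class holds one participant at each of three visits and none elsewhere. Then M = 1 and S = 3, so one, two or three participants were affected, and the table looks the same in each case.

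| Participants affected | Percent of 27 | Exact 95% interval |
|---|---|---|
| 1 | 3.7% | 0.09% to 18.97% |
| 2 | 7.4% | 0.91% to 24.29% |
| 3 | 11.1% | 2.35% to 29.16% |

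The ambiguity concerns losses that come and go. A loss that persists is counted at each later scheduled visit attended, including Month 12.

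**3. Class boundaries.** The SAP 15.1 classes, read literally, give:

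- -15 falls in both <=-15 and -15 to <-8;
- +8 falls in both >0 to 8 and >=8 to 15;
- +15 falls in both >=8 to 15 and >=15.

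So the count of 15-letter losses is ambiguous at exactly the value that defines it.

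**4. How often chance alone would flag an eye.** The documents give no test-retest SD for BCVA, so I assume a single-reading SD of 3, 4 or 5 letters, independent normal errors and no true change. Baseline is the mean of two readings (SAP 15.1). There are nine scheduled visits from Day 1 to Month 12. With b the error in the baseline mean, b ~ N(0, SD²/2), and Φ the standard normal distribution function:

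P(change <= -15 at any of 9 visits) = 1 - E_b{[1 - Φ((b - 15)/SD)]^9}

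P(change <= -15 at one given visit) = Φ(-15/(SD × √1.5))

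| Assumed SD | Any of 9 visits | Expected in 27 eyes | One given visit |
|---|---|---|---|
| 3 | 0.02% | 0.005 | 0.002% |
| 4 | 0.9% | 0.25 | 0.1% |
| 5 | 5.4% | 1.45 | 0.7% |

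If readings are rounded to whole letters, simulation raises the 5.4% to 6.0% (27 × 0.060 = 1.6 eyes). At SD 5, then, about one and a half of 27 study eyes would be flagged at some visit by measurement noise. A Month 12 count is much less exposed: 27 × 0.007 = 0.2 eyes.

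**The case against.** The case on the other side is substantial.

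- *Acuity loss can reach the safety tables.* In Protocol 7.2, principal does not mean exclusive. AEs are reviewed at every visit. Protocol 7.2.1.3 says to report an observation when in doubt, and 7.3.1 says to record a pre-existing condition that deteriorates. SAP 14.1 summarises ocular TEAEs separately for study and fellow eyes. A reader might infer that vision loss in the injected eye is never reported as a safety result; these provisions rule that out.
- *Individual losses are not hidden by averages.* A reader might worry that gains in other eyes cancel a loss: in a group of six, one eye at -20 and five at +4 give a mean of (-20 + 5 × 4)/6 = 0. But the minimum would show -20, Table 14.2.1.3 would show 1/6 in the lowest class, and the box plots, shift plots and listing would carry that eye. Only the mean cancels, and it is not shown alone.
- *A numerical AE rule may exist elsewhere.* CTCAE v4.0 and the Study Manual of Procedures accompany the protocol and are not available here. The documents therefore do not support the inference that sites have no guidance on size of loss, and the noise figures make a fixed letter threshold for AE recording debatable.
- *The monitoring committee is not confined to AEs.* Protocol 10.7.5 gives it a summary of all available data.
- *The count could be made by hand.* With about 27 participants, the acuity listing would allow it.

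All of this stands. What remains is that no planned table makes the count. A hand count from a listing after the data are known is weaker than a prespecified one, above all when the boundary value belongs to two classes.

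**Conclusion.** The point holds as a gap in reporting. Acuity has no safety table, and no planned table gives an any-visit or worst-value count of large losses, although two of the three examinations named in Protocol 7.2 are summarised by worst value. The safety tables show acuity loss only where it was recorded as an AE. Transient losses at different visits are not combined, and in the illustration 3/27 affected participants would show as at most 1/27 at any visit. That illustration is constructed: it assumes three participants, each with a loss at one different visit, and a denominator of 27.

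No planned analysis is invalid and no scheduled measurement is lost. Persistent losses and outlying eyes remain visible in the by-visit table, plots and listing. The change is worth making because safety is the primary objective and the data are already being collected.

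**What to change.** 1. Add one safety table to SAP Section 14: number and percent of participants with a BCVA loss of 15 or more letters from baseline (a) at any post-injection visit through Month 12, including unscheduled visits, and (b) at Month 12. Present it by group and overall, study eye beside fellow eye. State that this table is an exception to the SAP 9.4 rule on unscheduled visits.
2. Make the SAP 15.1 classes non-overlapping, so that a change of exactly -15 is counted once, in the <=-15 class. Settle +8 and +15 in the same way.
3. Optional: name BCVA among the methods for detecting ocular AEs in Protocol 7.2.

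**Cost.** One more table from data already collected, and an edit to one line of class limits. Some any-visit counts will reflect test variability (about 1.5 of 27 study eyes at an assumed SD of 5 letters, very few at SD 3), so the study-eye count should be read against the fellow-eye column. That background is approximate: the study eye is chosen as the worse-seeing eye at baseline, so the two eyes are not exchangeable.

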#### 7.2.1 Adverse Events and Serious Adverse Events

#### 7.2.1.1 Definition of an Adverse Event

The International Conference on Harmonisation (ICH) E6 Good Clinical Practice (GCP) guidelines define an AE as "any untoward medical occurrence in a patient or clinical investigation subject administered a pharmaceutical product and which does not necessarily have a causal relationship with this treatment." An AE can therefore be any unfavorable and unintended sign (including an abnormal laboratory finding), symptom, or disease temporally associated with the use of a medicinal (investigational) product. The occurrence of an AE may come to the attention of study personnel during study visits and interviews or by a study recipient presenting for medical care. All AEs must be graded for intensity and relationship to study product.

An AE **does** include:

- Exacerbation of a pre-existing illness,
- An increase in frequency or intensity of a pre-existing episodic event or condition,
- A condition detected or diagnosed after study agent administration even though it may have been present prior to the start of the study,
- Continuous persistent disease or symptoms present at baseline that worsen following the start of the study.

An AE does not include:

- A medical or surgical procedure (e.g., surgery, endoscopy, tooth extraction, transfusion); the condition that leads to the procedure may be an AE,
- A pre-existing disease or conditions present or detected at the start of the study that does not worsen,
- Situations where an untoward medical occurrence has not occurred (e.g., normal pregnancy, hospitalizations for cosmetic elective surgery, social and/or convenience admissions),
- Overdose of either study agent or concurrent medication without any signs or symptoms.

AEs may include pre- or post-treatment events that occur as a result of protocol-mandated procedures (e.g., invasive procedures, modification of subject's previous therapeutic regimen). Intercurrent illnesses that occur after screening but before starting treatment, and that are not the result of protocol-mandated procedures, do not need to be captured as AEs.

